2.3.1 Regimen Transition: Weekly Intravenous to Daily Oral Levosimendan

With Version 4.1, current patients may transition from intravenous (IV) levosimendan to oral levosimendan.

All patients that have signed consent will be transitioned from weekly IV levosimendan to daily oral levosimendan over a 6-week period, with visits every 2 weeks.

Unless otherwise noted, patients will continue to visit the investigational site at Weeks 3, 6, 12, 24, 48 and yearly through Follow-Up Visit (at termination) up/Termination visit per the date the patient first started the TNX-LVO-05 study (e.g., completion of the parent study).

2.4 Number and Type of Subjects

Patients who completed all study visits through the end of the parent study were eligible to enroll into the Open-Label extension study.

2.5 Investigational Product

Upon entry into the study, levosimendan was administered in open-label, intravenously at 0.075 µg/kg/min for 24 hours ±30 min, or as per directed by the treating physician. A physician was to assess the patient's safety at Week 3 and up-titrate to 0.1 µg/kg/min for 24 hours. The decision to increase the dose was to be based on the absence of disease or drug related adverse events and the investigator's discretion.

If a subject was down-titrated to 0.05 µg/kg/min in the TNX-LVO-04 study for either the Lead-In dose or during the double-blind portion of the study, the subject was to start at this dose, with the first opportunity to up-titrate following at Week 3.

All subjects will be transitioned to an oral dose of levosimendan once an informed consent form has been signed. Those currently receiving levosimendan IV weekly will return to the investigational site and receive 1mg levosimendan capsule daily for two weeks.

Subjects may then be titrated up every 2 weeks at 1mg levosimendan increments up to maximum of 4 mg daily (1mg QID), based on assessments of safety and patient's clinical response (see [Attachment 3 Cardiac Event Recommendations and Management](#)). Patients that tolerate 3 mg (1mg TID) oral levosimendan TID that have not demonstrated a 6MWD equivalent or better than the recorded 6MWD at initiation of their IV to oral levosimendan may be titrated to 4 mg (1mg QID). Patient's that experience identified safety concerns in Attachment 3 should be downtitrated at 1 mg/day increments or discontinued at the physician's discretion.

Once a patient completes the transition to oral levosimendan, all IV drug and ancillary supplies related to the administration of IV levosimendan will be returned to the central pharmacy for destruction.

At the initial visit of the IV to oral levosimendan transition, each patient will receive a supply of 1mg oral levosimendan capsules. Subsequent supplies may be shipped to the patient's home.

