Body Weight	X	X					X	X
Serum Chemistry and Hematology (Local Lab) ⁷	X	X			X ⁶	X	X	X
Child Pugh Class ⁷	X							X
Vital Signs	X	X	X	X	X	X	X	X
Pharmacokinetic Sample		X ²		X	X ²	X ²		
Electrocardiogram (ECG)	X	X			X ⁶	X		X
Levosimendan Administration (oral) / Dose Titration ³		X	X	X	X ⁴			
NYHA Functional Class	X	X			X ⁶	X	X	X
6 - Minute Walk Test	X	X			X ⁶	X	X	X
Adverse Events/SAEs ⁸	X	X	X	X	X	X	X	X
Concomitant procedures and medications	X	X	X	X	X	X	X	X
KCCQ Assessment ⁹	X	X			X ⁶	X	X	X

Footnotes for Time and Events Schedule

1. Visits will be scheduled 7-9 days following completion of the levosimendan IV dose and every 14 days through the oral levosimendan transition (+/- 48 hrs); at the Investigator's discretion, Week 2 and 4 visits may be performed remotely.
2. Blood sample to be taken prior to the patient's daily dose of oral levosimendan.
3. The first dose of oral levosimendan to be taken 7-9 days after the patient's final weekly IV levosimendan dose. Once oral levosimendan begins, subjects must completely discontinue weekly levosimendan infusions. Patients will begin a daily dose regimen of 1mg daily and titrated at 1mg increments every 2 weeks, as tolerated.
4. At the investigator's discretion, patients that have not demonstrated an adequate response to drug therapy and a tolerance to the 1mg levosimendan TID may be titrated to 1mg QID. Patients that have not tolerated 1 mg levosimendan TID should be down titrated to 1mg BID. All patients that are titrated at Week 6 should return for a Week 8 visit.
5. Due to the COVID-19 pandemic, the investigator may have a phone conversation with the patient rather than having the patient come in for an office visit. The phone conversation should include the following, as reported by the patient; adverse events, concomitant medications (new or changed), concomitant procedures, and blood pressure & heart rate (use provided home blood pressure cuff).
6. If a patient is up or down titrated and therefore scheduled for a Week 8 visit, these procedures do not need to be performed at Week 6.
7. Local labs will be drawn (including NT-proBNP). Child-Pugh Class is only required for patients with documented liver disease.
8. During routine visits and throughout a participation in the study, patients should be queried for any new or changes to AEs, concomitant medications, concomitant procedures, hospitalizations, and/or emergency room visits

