Importantly, levosimendan-treatment resulted in significant reductions in resting mPAP and RAP, two hemodynamic measures that have been shown to be highly correlated with mortality in PH patients. The change from baseline to Week 6 in mPAP and RAP measured at rest was -5.43 mmHg, $p=0.0003$ and -4.50 mmHg, $p=0.0004$, respectively. These hemodynamic effects appear the result of K-ATP activation and independent of the drug's inotropic activity, as the CI of levosimendan-treated patients was unchanged. A detailed analysis of the mechanism of action looking at noninvasive pressure/volume relationships did not demonstrate any inotropic effects following the initial 24-hour infusion of levosimendan. Rather, the data support that effects on the estimated stress blood volume may be important.

Patients receiving levosimendan also had a statistically significant, and clinically significant, improvement in exercise capacity over placebo as measured by their 6MWD (29.3 meters (2.5, 56.1 95%CI) $p=0.0329$. 6MWD did not differ at baseline but decreased by an average of -12.7 meters in the placebo group and increased by an average of 16.6 in the levosimendan.

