1.3.8 Target Plasma Concentrations of OR-1896 in chronic treatment of PH-HFpEF Patients

Levosimendan represents an active prodrug to the active metabolite OR-1896 with extended pharmacodynamic effects that parallel those of levosimendan. The elimination half-life of levosimendan itself is short (approximately 1 hour), whereas that of the metabolite OR-1896 is long (70-80 hours in heart failure subjects). During a long-term oral dosing of levosimendan with constant daily dose, the OR-1896 plasma levels achieve a steady-state with minimal daily variation.

The chronically active moiety of levosimendan administration is the metabolite OR-1896. Levosimendan is cleared within 5 hours of ending an infusion.

The wide range of OR-1896 concentrations observed in daily oral levosimendan dosing (PERSIST study, see Section 1.3.4) and weekly IV administration (HELP Study, Section 1.3.5) precludes the identification of a specific oral dose to be used in the IV to oral transition. Importantly, the range of OR-1896 plasma concentrations observed in the PERSIST study of class IIIb-IV CHF patients overlap those observed in the HELP Study of PH-HFpEF patients (Figure 3).

[figure not shown]

Figure 3. Comparison of OR-1896 Plasma Concentrations in PERSIST Study of Daily Oral Levosimendan (1mg QD, 1 mg BID) versus the HELP Study of Weekly IV Levosimendan (0.1 ug/kg/min for 24 hrs).

However, only one third of the HELP Study patients were sampled at peak OR-1896 levels, 2-3 days following their previous levosimendan IV dose. The remaining patients were sampled beyond the period of peak OR-1896 concentrations observed in a weekly IV levosimendan regimen. An opportunity to titrate patients to 4 mg total daily dose (1mg QID), as tolerated based on blood pressure and heart rate, will ensure all transitioning patients will achieve adequate steady state levels of OR-1896.

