1.3.8.3 Individualized Oral Dose Regimen

The broad range of observed OR-1896 concentrations in the HELP and PERSIST studies indicates a personalized daily dose may improve individual patient response to levosimendan and its active metabolite OR-1896. The wide range in plasma levels of OR-1896 observed in the HELP and PERSIST studies indicate steady state concentrations from daily dosing will be somewhat independent of body weight or the severity of CHF. The transition from IV to oral levosimendan provides an opportunity for personalized dosing based on patient tolerability.

The step wise increases from 1mg up to 4mg daily levosimendan doses will be based on tolerability of the therapy. Heart rates and blood pressures will be monitored and recorded by the patient each day. Guidance will be provided to ensure measurements are standardized at rest during the same approximate time each day. Investigators will review the heart rate and blood measure measurements to ensure the patient has tolerated their current levosimendan dose and guide the titration (up or down) according to [Attachment 3 Cardiac Event Recommendations and Management](#) and investigator judgment.

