5.5 Oral Levosimendan

5.5.1 Dosage and Administration

Dosing Regimen: Subjects will start with a 1 mg levosimendan dose (in the morning) for 2 weeks. If tolerated, the dose will be increased after 2 weeks to 1 mg BID, after 4 weeks to 1mg TID, and after 6 weeks (if applicable)¹ to 1mg QID. The titration sequence is as follows:

Previous IV Infusion	Week 0 (Office)	Week 2 (Home)	Week 4 (Home)	Final Visit Week 6 (Office)	Week 8 (Office)
----------------------	-----------------	---------------	---------------	-----------------------------	-----------------

0.10 µg/kg/min	1mg QD (1mg total daily dose) Morning	1mg BID (2mg total daily dose) Every 12 hrs.	1mg TID (3mg total daily dose) Every 8 hrs.	Patient evaluated for further titration (up or down) ¹	Only patients titrated (up or down) at Week 6 No further dose titration above 4mg QID
----------------	---	--	---	---	---

¹ At the investigator's discretion, patients that have not demonstrated an adequate response to drug therapy and a tolerance to the 1mg levosimendan TID may be titrated to 1mg QID. Patients that have not tolerated 1 mg levosimendan TID should be down titrated to 1mg BID. All patients that are titrated at Week 6 should return for a Week 8 visit.

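### The criterion for the Week 6 step from 1 mg TID to 1 mg QID differs between sections, and the walk test that one wording depends on can be skipped in the patients it selects

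*Protocol*

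**What the plan says.** The oral regimen rises by 1 mg/day every two weeks, reaching 1 mg TID at Week 4. Whether to go on to 1 mg QID is decided at Week 6. The condition for that last step is worded in three ways.

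- **Walk distance.** Protocol 2.5 offers it to "Patients that tolerate 3 mg (1mg TID) oral levosimendan TID that have not demonstrated a 6MWD equivalent or better than the recorded 6MWD" at the start of the transition. SAP 2.2.3 repeats the rule.
- **Judged response.** Protocol 5.5.1 footnote 1, and the same text in Time and Events footnote 4, leaves the decision to the investigator and says that "patients that have not demonstrated an adequate response to drug therapy and a tolerance to the 1mg levosimendan TID may be titrated to 1mg QID". The sentence that follows sends patients who have not tolerated TID down to BID.
- **Tolerability only.** Protocol 1.3.8 describes "An opportunity to titrate patients to 4 mg total daily dose (1mg QID), as tolerated based on blood pressure and heart rate", and 1.3.8.3 says that "The step wise increases from 1mg up to 4mg daily levosimendan doses will be based on tolerability of the therapy". The Synopsis and Schedule footnote 3 also name tolerability and no response condition.

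On measurement, the Schedule marks the Week 6 walk test with footnote 6. For a patient titrated at Week 6 and so due back at Week 8, that footnote says "these procedures do not need to be performed at Week 6".

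**The concern.** This is the step to the highest oral dose in the study, so a site needs one rule for it. As written, a site working from Section 2.5 compares two walk distances. A site working from 5.5.1 or the Schedule asks whether response is adequate, with no measure named. A site relying on Section 1.3.8.3 or the Synopsis sees tolerability alone. The dose a patient ends on could then depend on which page was read.

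Two further defects sit alongside. The negation in footnote 1 can be read grammatically to cover tolerance as well as response. And the walk test that Section 2.5 relies on is waived for the patients whose dose changes at that visit. What is at stake is consistent handling of the top dose across sites, and knowing what being on 4 mg/day says about a patient when doses and safety are described.

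**Working it through.** The plan states no figure for the share of patients expected to reach QID, so there is nothing to reproduce. The check is a comparison of passages, then a test of whether the difference can be sized.

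**1. The conditions side by side**

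| Where | Condition for QID | Measure | Left undefined |
|---|---|---|---|
| Protocol 2.5; SAP 2.2.3 | Tolerates TID and walk distance falls short of the transition-start value | 6MWD against Week 0 | Margin for *equivalent* |
| Protocol 5.5.1 fn 1; Schedule fn 4 | Response inadequate, with tolerance of TID | Investigator's judgment | What response is; reach of the negation |
| Protocol 1.3.8, 1.3.8.3; Synopsis; Schedule fn 3 | Tolerability | Blood pressure and heart rate (1.3.8) | Whether any response condition applies |

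**2. Do they pick the same patients?** Take two patients who both tolerate TID.
- The first walks further than at Week 0, but the investigator regards the overall response as inadequate. Section 2.5 does not select this patient; footnote 1 does; the tolerability wording does.
- The second walks slightly less far, but the investigator regards the response as adequate. Section 2.5 selects this patient if *equivalent* means no margin; footnote 1 does not; the tolerability wording does.

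So the wordings are not interchangeable unless response is defined as 6MWD, which no passage says.

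**3. Is the walk test available when needed?**
- The Schedule has transition walk tests at Week 0, Week 6 and Week 8, and none at Weeks 2 and 4. TID starts at Week 4, so Week 6 is the first scheduled transition walk test on TID.
- Footnote 6 waives it for anyone titrated up or down at Week 6. Section 7.1.4 lists it with no exception.
- The logic is circular: under Section 2.5 the walk test decides the titration, while under footnote 6 the titration decides whether the walk test is needed.
- Section 7.1.5 lists the walk test at Week 8, then says it need not be done for patients scheduled for Week 8. This may be the Week 6 waiver in the wrong place. As printed, a titrated patient could have no walk test at either visit.
- A Week 8 test comes after the dose change, so it cannot inform the Week 6 decision. A routine office visit, timed from entry into the study, could supply one only by coincidence.

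**4. Can the difference in who is eligible be sized?** The only usable walk data are from the parent study (Protocol 1.3.5): difference 29.3 m, 95% CI 2.5 to 56.1, arms of 18 and 19, mean changes +16.6 m and -12.7 m.
- SE = (56.1 - 2.5) / (2 × t(0.975, 35)) = 53.6 / (2 × 2.03) = 13.2 m.
- SD = 13.2 / √(1/18 + 1/19) = 40.1 m. These inputs agree with each other: 16.6 + 12.7 = 29.3, and the implied p is 0.033 against the stated 0.0329.
- Assuming normal changes, share below Week 0 = Φ((-margin - mean)/SD). The gap from the tolerability wording among TID tolerators is 1 minus that share.

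| Assumption (SD 40 m) | Gap, tolerability v. 6MWD wording |
|---|---|
| No margin; mean -12.7, 0, +16.6 m | 37.5, 50.0, 66.1 points |
| 30 m margin for *equivalent*; same means | 66.7 to 87.8 points |
| No margin; 50% to 85% of all transitioned patients tolerate TID | 18.8 to 56.2 points |
| Judged-response wording instead of 6MWD, share q unknown | 100 × (1 - q): 0 to 100 points |

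The answer is driven by the assumptions. None of the margin, the tolerating share, q, or the distribution of walk change over the IV-to-oral switch is in the documents.

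**The case against.** The strongest reply is that the passages governing this step largely agree. Sections 1.3.8 and 1.3.8.3 are background, the Synopsis gives a ceiling, and Schedule footnote 3 is general. The Week 6 titration cell carries footnote 4, and the main text of 5.5.1 makes QID conditional and points to footnote 1. The specific passages (2.5, SAP 2.2.3, 5.5.1 footnote 1, Schedule footnote 4) all pair tolerance with insufficient response. Section 2.5 also introduces titration as resting on safety and clinical response, so its walk-distance sentence may simply say how response is judged. This stands in part: it rules out reading the protocol as sending every tolerating patient to QID, since the wording is permissive or speaks of an opportunity. It does not show that 6MWD is the response measure in footnote 1, because no passage links the two.

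On the negation, the next sentence of the footnote, the opening condition of Section 2.5 and the dose-limiting events in Attachment 3 all point away from raising the dose in patients who do not tolerate TID. A reader might infer that the protocol permits it; read as a whole, it does not. What remains is a drafting fault in an escalation rule, printed twice.

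On the waiver, footnote 6 does not forbid the walk test, and a careful site could do it before deciding. That is true, but nothing requires it.

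On analysis, SAP 3.1.5 plans no hypothesis test, SAP 3.4.3 no subgroup analysis, and SAP 3.2.1 summarises by IV period, oral period and total. No contrast of 3 mg with 4 mg is specified, and individualised dosing would confound one under any single rule. This stands.

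**Conclusion.** The inconsistency is real and should be corrected. The operative passages give sites different conditions for the highest oral dose, two key terms are undefined, and the walk-distance wording can lack its own measurement at the moment of decision. This bears on patient safety and on consistency between sites.

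The size of the effect cannot be derived from the documents. A reader might infer from the parent-study walk data that the wordings differ by some tens of percentage points in who reaches QID. That compares only two of the three wordings and carries parent-study changes over to a different switch. It also depends on an assumed margin and tolerance rate, and it measures eligibility rather than titration.

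A reader might also infer that results by dose become uninterpretable. That goes too far. Protocol 10.6 counts patients at each dose by visit, and several SAP sections refer to treatment/dose group, so the make-up of the 4 mg group would be less clear. No planned comparison, test or power statement depends on it.

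The SAP says it follows protocol v5.0, while the protocol reviewed here is Version 4.1. Whether v5.0 changed the dosing text cannot be seen, but the SAP still carries the walk-distance wording. No view is taken on which criterion is right.

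**What to change.** The sponsor and investigators should reconcile Protocol 1.3.8, 1.3.8.3, 2.5, 5.5.1 with its footnote 1, the Synopsis, Schedule footnotes 3 and 4, and SAP 2.2.3, so that one criterion of their choosing appears throughout. In doing so:

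- Say whether 6MWD is the response measure. If it is, state what *equivalent* means; if not, define adequate response.
- Reword footnote 1 and Schedule footnote 4 so that the negation covers response only and tolerance of TID is a separate condition.
- Align Schedule footnote 6 with Sections 7.1.4 and 7.1.5, so that any measurement the rule needs is taken before the Week 6 decision and the Week 8 requirement is unambiguous.

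Optionally, record on the eCRF the reason for each Week 6 dose decision, so that patients who reached 4 mg for different reasons can be told apart.

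The cost is a clarification letter or amendment, a matching SAP edit, and one eCRF field if the optional item is taken up. There are no extra visits. If 6MWD is retained as the criterion, the Week 6 walk test becomes required at a visit already scheduled.

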2.6 Sites and Regions

This study will be conducted at any site that participated in the parent study and has ongoing patients.

3. STUDY POPULATION

3.1 Inclusion Criteria

Diagnosis and main criteria for inclusion and exclusion:

Patients must meet the following criteria to be continued in the study:

Enrollment Criteria:

1. Provide a personally signed and dated informed consent document prior to initiation of any study-related procedures that are not considered standard of care.
2. Completed double-blind therapy in a PH-HFpEF clinical study sponsored by Tenax Therapeutics, Inc.
3. May, in the opinion of the Investigator, benefit from continued levosimendan treatment.
4. Female patients of childbearing potential must agree to use a highly effective method of contraception.
5. Willingness and ability to comply with scheduled visits, treatment plan, laboratory tests and other study procedures.

3.2 Exclusion Criteria

Subjects are excluded from the study if any of the following exclusion criteria are met.

1. Discontinued treatment in the parent study for any reason other than study completion or Sponsor termination of the study.
2. Pregnant or breastfeeding women.
3. Local access to commercially available levosimendan.
4. Inability to comply with planned study procedures
5. Patients with scheduled lung or heart transplant or cardiac surgery
6. Dialysis developed since enrollment in parent study (either hemodialysis, peritoneal dialysis, continuous venovenous hemofiltration, or ultrafiltration)

7. Estimated glomerular filtration rate (eGFR) < 30 mL/min/1.73m²
8. Liver dysfunction with Child Pugh Class B or C (see [Attachment 1](#))
9. Evidence of systemic bacterial, systemic fungal, or viral infection refractory to treatment
10. Weight > 150 kg
11. Systolic blood pressure (SBP) cannot be managed to ensure $SBP \geq 100$ mmHg at initiation of study drug
12. Heart rate ≥ 100 bpm with study drug, persistent for at least 10 minutes at screening.
13. Hemoglobin < 80 g/L
14. Serum potassium < 3.0 mmol/L or > 5.5 mmol/L at baseline that is unresponsive to management

3.3 Restrictions

Potential subjects must be willing to adhere to the following prohibitions and restrictions during the study to be eligible for participation.

- Women of childbearing potential only must agree to remain on an effective method of birth control or remain abstinent throughout the study.
- Medication or treatment for heart failure or respiratory disease must be maintained during the trial, unless contraindicated

3.4 Withdrawal of Subjects

A subject may withdraw from the study at any time for any reason without prejudice to their future medical care by the physician or at the institution. The Investigator or Sponsor may withdraw the subject at any time (e.g., in the interest of subject safety). The withdrawal of a subject from the investigational product by the Investigator should be discussed where possible with the Medical Monitor and/or Sponsor before the subject stops investigational product.

If the investigational product is discontinued, regardless of the reason, the final evaluations are to be performed as completely as possible. Whenever possible, all discontinued subjects should also undergo the protocol-specified Follow-Up Visit (at termination) evaluations. Comments (spontaneous or elicited) or complaints made by the subject must be recorded in the source documents. The reason for termination, date of stopping investigational product, and the total amount of investigational product taken must be recorded on the Case Report Form (eCRF) and source documents.

